3.3. Benefit-Risk Assessment

The potential benefit of BIIB105 in ALS has not been established. This study has been designed with appropriate dose escalation, safety monitoring, and stopping rules to minimize risks to participants. The results of this study may offer key insights into the development of a disease-modifying therapy for ALS.

This is a first in human study, thus the risk in humans is unknown. Emerging clinical data can be found in the Investigator's Brochure.

Nonclinical work with *Atxn2* homozygous knockout mice suggests that ATXN2 reduction could be associated with risks of metabolic complications (adult-onset obesity and insulin resistance) and subtle neurological deficits [Huynh 2009; Kiehl 2006; Lastres-Becker 2008]. Human data from the Genome-Wide Association Studies database suggest that variation in *ATXN2* could be associated with changes in blood pressure and cardiometabolic phenotypes [Auburger 2014]. From the nonclinical safety studies in NHPs, the adverse effect level was considered to be mg based on severe but reversible and monitorable clinical signs: 1 of 3 animals exhibited increased muscle tone, whole body spasms, and tremors that required administration of diazepam. The animal fully recovered by hours. No adverse metabolic effects were seen in toxicology studies. Participants will be monitored in the clinical setting with neurological and physical examinations and careful monitoring of blood chemistries, among other safety assessments.

Although LP is generally considered a safe procedure, certain complications can occur in a subset of patients. These may include, but are not limited to, back pain, headache, nausea, infection, bleeding, radicular pain and numbness, and bruising or injury at the injection site. These potential risks can be mitigated by using atraumatic needles, avoiding contraindicated medications, and testing coagulation and platelet counts prior to the procedure. Importantly, life-threatening cerebral herniation is a possible complication of a lumbar puncture procedure.

Reproductive toxicity studies were conducted in mice and rabbits using SC administration of BIIB105 once every other day. In a definitive combined fertility and embryo-fetal development

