⁸On dosing days, to be assessed predose and at 3 and 6 hours postdose. At UV, a limited neurological examination may be performed per the Investigator's discretion.

⁹On dosing days, ECG and vital signs are to be assessed just prior to drawing PK blood samples at predose, and 2 and 4 hours postdose. Vital signs may be measured in either the sitting or supine position, and ECGs are to be done in triplicate after resting in the supine position for ≥ 5 minutes. During UV, ECGs are to be done if medically indicated. All ECGs will be read by the Investigator at collection and then sent to a central ECG reader for further evaluation and to confirm eligibility at Screening.

¹⁰ On dosing days, to be performed before dosing.

¹² Administered by LP.

CONFIDENTIAL

The information contained herein may not be used, disclosed, or published without the written consent of Biogen MA Inc.

¹³ Use “Since Last Visit” version of C-SSRS from Day 8 onward. Done predose on dosing days. At UV, may be assessed per the Investigator’s discretion.

¹⁴ HbA1c and lipid panel to be assessed at Screening and on Days 1, 85, and 175 only.

¹⁵ To be collected predose and at 1, 2, 4, and 6 hours postdose on dosing days.

¹⁶ To be collected predose on dosing days. Collected by LP. Participants to be observed in the clinic for ~6 hours after the LP procedure on dosing days and for ~1 hour on nondosing days.

CONFIDENTIAL

The information contained herein may not be used, disclosed, or published without the written consent of Biogen MA Inc.

Table 2: Part 1 Schedule of Activities: Cohort D1 and D2

	Screening ¹	Dose 1 (Inpatient)														FU Period ²		UV				
				CV	Dose 2	TC	CV	Dose 3	TC	CV	TC	Doses 4, 5, 6, 7	TC	CV	TC	Dose 8	TC	CV	TC			
Days	1	2	8	15 (±2)	16 (±3)	22 (+1) ⁴	29 (±3)	30 (+1) ⁴	36 (±3)	50 (±3)	57, 85, 113, 141 (±3)	58, 86, 114, 142 (+1) ⁴	64, 92, 120, 148 (±3)	78, 106, 134, 162 (±3)	169 (±3) ³	170 (+1) ⁴	176 (±3)	177 (+1) ⁴	214 (±3)	215 (+1) ⁴	259 (±3)	260 (+1) ⁴
Assessments ⁵	-28 to -1	Predose	Dosing/Postdose (24±1 h) postdose																			
ICF (Main)	X																					
ICF (Informant/ Caregiver) ⁶	X																					
Eligibility Criteria	X																					
Demographics	X																					
Medical History	X	X																				
Confirmation of ALS Diagnosis	X																					
Blood Sample for DNA (assessment of polyQ status and ALS- causative genes)	X																					
Clinical Laboratory Samples for Viral Serology ⁷	X																					

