5.7.2. Laboratory Data

Laboratory data will be evaluated to determine the incidence of abnormalities that emerge during the study. Changes in laboratory evaluations will be presented relative to baseline, which is defined as the closest visit prior to the subject start treatment. Baseline value is defined as data collected which are prior to and/or on the date of the first dose, usually also the same day as the Day 1 visit. If there is more than one value on or before Day 1, then the last non-missing value prior to (including on) the date of first dose will be used as the baseline value.

The following clinical laboratory parameters are assessed in the protocol:

- Hematology panel: complete blood count with differential
- Blood chemistry panel: total protein, albumin, HbA1c, lipid panel, creatinine, blood urea nitrogen, uric acid, bilirubin (total and direct), alkaline phosphatase, alanine aminotransferase, aspartate aminotransferase, gamma-glutamyl transferase, glucose, calcium, phosphorus, bicarbonate, chloride, sodium, and potassium
- Urinalysis: Dipstick for blood, protein, and glucose (microscopic examination, if abnormal)
- CSF analysis: red blood cell count, white blood cell count, protein, and glucose.
- Coagulation: PT (prothrombin time), aPTT (activated partial thromboplastin time), and INR (international normalized ratio).

CONFIDENTIAL

The information contained herein may not be used, disclosed, or published without the written consent of Biogen MA Inc.

Shift analyses

Each hematology, blood chemistry, coagulation and CSF laboratory parameter will be flagged as “low” or “high” relative to the parameter’s normal range or as “unknown” if no results is available. All visits with available results, including unscheduled visits, will be included in shift analysis.

For each urinalysis laboratory parameter, the number and percentage of participants experiencing post-dosing shifts to abnormal will be summarized.

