For each hematology, blood chemistry, coagulation and CSF laboratory, the number and percentage of participants experiencing post-dosing shifts to “low” or “high” will be summarized. Shift to low includes results from normal to low, high to low, and unknown to low. Shift to high includes results from normal to high, low to high, and unknown to high. In each summary, the denominator for the percentage is the number of participants at risk for the shift. The number at risk for the shift to low is the number of participants whose baseline values is not low and who have at least one post-baseline value. The number at risk for the shift to high is the number of participants whose baseline value is not high and who have at least one post-baseline value. A participant will be counted only once for each parameter and each type of shift if there are more than one occurrence for that parameter and that type of shift among post-dosing assessments. Participants with shift will be listed by laboratory parameter and shift type.

Summary of change from baseline and other analysis

In addition to the shift analysis, descriptive statistics (N, mean, SD, median, 1st and 3rd quartiles, and minimum and maximum values) for observed laboratory values, change from baseline and percentage change from baseline in laboratory values of hematology, blood chemistry, and coagulation will be summarized by treatment group and visit. Line plots showing mean and change from baseline value for each treatment over visits will also be presented. Only scheduled visits will be included in these summaries. Spaghetti plots by site will be presented for CSF samples. Proportion of participants with CSF WBC values above 5, 10, and 20 10⁶/L and proportion of participants with CSF protein level above 4X, 3X, and 2X ULN (upper limit of normal) will be summarized.

Listing of all chemistry, hematology, coagulation, CSF, and urinalysis values will be provided. Abnormal values will be flagged.

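### The CSF white-cell threshold counts make no use of the red-cell count from the same sample, so blood from a traumatic lumbar puncture can inflate them in every arm

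*SAP*

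**What the plan says.** The CSF safety panel in section 5.7.2 of the Part 1 SAP is "CSF analysis: red blood cell count, white blood cell count, protein, and glucose". The same section then plans two sets of threshold summaries: "Proportion of participants with CSF WBC values above 5, 10, and 20" x10^6/L, and "proportion of participants with CSF protein level above 4X, 3X, and 2X ULN". Neither carries a condition on red cells.

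Red cells enter the plan in two other ways. They are a CSF parameter in the shift analysis ("For each hematology, blood chemistry, coagulation and CSF laboratory, the number and percentage of participants experiencing post-dosing shifts to" low or high), and they appear in the listings ("Listing of all chemistry, hematology, coagulation, CSF, and urinalysis values will be provided", with abnormal values flagged). CSF samples are also plotted by site.

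On sampling, the schedule footnote reads "To be collected predose on dosing days. Collected by LP". Protocol section 3.3 says of lumbar puncture complications: "These may include, but are not limited to, back pain, headache, nausea, infection, bleeding".

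Section 5.7.2 of the final SAP repeats the white-cell cut-offs. The rest of that sentence is redacted. Its Table 5 plans a post-baseline evaluation of CSF white cells and protein for both Part 2 dose columns and all three integrated pools; none of these is a placebo column.

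**The concern.** Blood that enters a CSF sample during the puncture brings its own white cells. The lowest cut-off, 5 x10^6/L, is low enough for a bloody sample to cross it with no change in the participant's CSF. A count that ignores red cells cannot separate the two cases.

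These counts carry some weight. The by-visit descriptive statistics in section 5.7.2 cover hematology, chemistry and coagulation but not CSF, so shift tables and threshold proportions are the main tabulated CSF safety results. The opening of section 5.7 of the final SAP names only adverse events and CSF laboratory data as evaluated for safety. Protocol section 3.2.3.1 also reports systemic and CNS inflammatory changes in one animal of the 41-week monkey study, judged nonadverse.

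In Part 1 the risk is a blurred comparison with placebo. In the final SAP it is a proportion with no comparator to show how much of it comes from the procedure.

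**Working it through.** The plan states no figure on this point, so there is nothing to reproduce. The check has four steps.

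**1. Are the inputs for a correction collected?** In the schedule tables (protocol Tables 1 to 3), every visit with CSF sampling also has a hematology sample. CSF red cells are in the CSF panel. So CSF WBC, CSF RBC, blood WBC and blood RBC are all available for each visit.

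**2. How much blood reaches a cut-off?** The documents give no blood cell ratio, so a range is assumed: one white cell per 500, 750 or 1,000 red cells. Starting from zero CSF white cells, RBC needed = cut-off x ratio.

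| Cut-off (WBC x10^6/L) | 1:500 | 1:750 | 1:1,000 |
|---|---|---|---|
| 5 | 2,500 | 3,750 | 5,000 |
| 10 | 5,000 | 7,500 | 10,000 |
| 20 | 10,000 | 15,000 | 20,000 |

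(RBC x10^6/L.) Contamination therefore bears mostly on the cut-off of 5. The cut-off of 20 needs four times as much blood.

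**3. How many participants could be counted?** Scheduled post-baseline CSF samples in Part 1:
- Cohorts A, B, C1, C2: Days 15, 29, 57, 85, 92, 130, 175, which is 7.
- Cohorts D1, D2 entering Part 2: Days 15, 29, 57, 85, 113, 141, 169, which is 7.

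Let p be the share of punctures bloody enough to exceed 5. The documents give no value, so 2%, 5% and 10% are assumed. If punctures are independent and the count is ever post-baseline, the share counted at least once is f = 1 - (1 - p)^7.

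- p = 2%: 1 - 0.98^7 = 13.2%
- p = 5%: 1 - 0.95^7 = 30.2%
- p = 10%: 1 - 0.90^7 = 52.2%

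If the proportion is by visit, contamination does not accumulate, and the share at each visit is p itself (2%, 5%, 10%). If bloody punctures cluster fully in the same participants, the ever count also falls back to p. The range at each p is thus 2% to 13%, 5% to 30% and 10% to 52%.

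**4. What does this do to the comparison with placebo?** Both arms have the same puncture schedule. Let true rates be a (active) and c (placebo), with a share f of true negatives falsely counted in each arm. The observed difference is

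[a + (1 - a)f] - [c + (1 - c)f] = (a - c)(1 - f).

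With assumed true rates of 40% and 10% (30 points):
- f = 10%: 46% against 19%, difference 27 points.
- f = 30%: 58% against 37%, difference 21 points.

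Equal contamination raises both proportions and shrinks the difference. It does not create one.

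**The case against.** The strongest reply is that the plan already limits the harm. Red cells have their own shift table, participants with shifts are listed, every CSF value is listed, and events related to lumbar puncture are tabulated separately. In Part 1 the placebo participants undergo the same punctures, so no false drug signal arises. This largely stands for Part 1 and keeps the point modest. It does not remove it. A red-cell shift is recorded once per participant and does not show whether the bloody sample was the one with the high white count; only reading the listings by hand would. The final SAP has no placebo column.

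Four stronger readings are tempting, and the documents do not support them.

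- *That the SAPs report contamination as CSF inflammation.* Neither visible CSF section uses that label or attributes the counts to the drug.
- *That the final SAP certainly has no red-cell rule.* The redaction falls directly after the cut-offs, so only the visible text can be judged.
- *That almost everyone would be flagged over the roughly 41 Part 2 doses.* The last scheduled maintenance day is 1093. Part 2 was introduced by protocol Version 3.0 of 18 November 2021. The final SAP is dated 05 September 2024, 1,022 days later, and records early termination. No participant could have completed that schedule by then.
- *That the protein counts are affected in the same way.* With an assumed blood count of 7 WBC to 4,700 RBC, 5 white cells correspond to 5 x 4,700 / 7 = 3,357 RBC x10^6/L. That is 3,357 / 4,700,000, or about 0.07% blood. At an assumed plasma protein of 7,000 mg/dL this adds about 5 mg/dL. With an assumed upper limit of normal of 40 to 60 mg/dL, that would not carry a normal sample past twice the limit.

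**Conclusion.** The point holds for the white-cell counts. The Part 1 SAP tabulates them without the red-cell result from the same sample, so blood from the puncture can inflate the proportions in all arms and dilute a difference from placebo by the factor (1 - f). For the final SAP the same holds on the visible text only, and inflation there would have no comparator to reveal it.

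The size is unknown. The 13%, 30% and 52% rest on assumed rates of 2%, 5% and 10% per puncture, on independent punctures, and on reading the proportion as ever post-baseline. The SAP does not state that reading, and the gap needs closing in its own right. These are descriptive safety tables. The point warrants an added sensitivity analysis; it does not invalidate the planned summary.

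**What to change.** 1. Keep the raw white-cell counts as the main table. State whether each proportion is by visit or ever post-baseline.
2. Add one prespecified sensitivity table that repeats the counts above 5, 10 and 20 in two ways:
   - (a) on corrected values, CSF WBC - CSF RBC x (blood WBC / blood RBC), using the blood count from the same visit;
   - (b) excluding samples above a CSF red-cell cut-off that the sponsor sets and justifies in advance.
3. Read this table beside the raw counts and not in place of them. In a first-in-human safety summary, an approximate subtraction could hide a true rise in white cells.
4. Do the same in the final SAP if its redacted text does not already cover it.

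The cost is SAP wording and one extra table per SAP. All inputs are already scheduled, and no procedure, dose or data collection changes. The main limitation is that the correction is approximate: under protocol section 15.1.5, CSF is analysed at local laboratories and hematology at a central one, so the formula mixes laboratories.

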5.7.3. Vital Signs

Summary statistical for actual values and change from baseline will be presented for each visit and vital sign parameters (temperature, pulse rate, respiratory rate, systolic and diastolic blood pressure). Weight will be summarized along with vital signs.

The incidence of clinically significant post baseline abnormalities will be summarized per the criteria below:

CONFIDENTIAL

The information contained herein may not be used, disclosed, or published without the written consent of Biogen MA Inc.

- Temperature <36°C or >38°C
- Weight 7% or more increase from baseline; 7% or more decrease from baseline
- Systolic blood pressure <90 mmHg or >140 mmHg or >160 mmHg
- Diastolic blood pressure <50 mmHg or >90 mmHg or >100 mmHg
- Pulse rate <60 beats/minute or >100 beats/minute
- Respiratory rate <12 breaths/min or >20 breaths/min

A listing of vital sign data will be provided.

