Study assessments conducted at each visit are listed in Table 1.

Duration of Study Participation:

Part 1:

Study duration for each participant in Cohorts A, B, C1, and C2 will be approximately 29 weeks:

4-week Screening Period

13-week Treatment Period

Approximately 12-week Follow-up Period

Study duration for each participant in D1 and D2 will be between approximately 29 and 41 weeks:

4-week Screening Period

25-week Treatment Period

Approximately 12-week Follow-up Period (only completed if the participant does not enter Part 2 after the Treatment Period)

Part 2:

Study duration for all participants will be up to approximately 172 weeks:

4-week Screening Period (for participants from Cohorts D1 and D2, Screening Period begins with Day 169 Visit of Part 1)

Up to approximately 156-week Treatment Period: either 104 weeks, or until the last participant enrolled has had the opportunity for their Part 2 Day 365 visit (Week 52), whichever occurs later.

Approximately 12-week Follow-up Period

Benefit-Risk Analysis:

The potential benefit of BIIB105 in ALS has not been established. The study has been designed with appropriate dose escalation, safety monitoring, and stopping rules to minimize risks to participants. The results of this study may offer key insights into the development of a disease-modifying therapy for ALS.

This is a first in human study, thus the risk in humans is unknown. Emerging clinical data can be found in the Investigator's Brochure.

Nonclinical work with *Atxn2* homozygous knockout mice suggests that ATXN2 reduction could be associated with risks of metabolic complications (adult-onset obesity and insulin resistance) and subtle neurological deficits such as motor hyperactivity and abnormal fear conditioning [Huynh 2009; Kiehl 2006; Lastres-Becker 2008]. Human data from the Genome-Wide Association Studies database suggest that variation in ATXN2 could be associated with changes in blood pressure and cardiometabolic phenotypes [Auburger 2014]. From the nonclinical safety studies in NHPs, the adverse effect level was considered to be mg based on severe but reversible and monitorable clinical signs: 1 of 3 animals exhibited increased muscle tone, whole body spasms, and tremors that required

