5.7.4. ECG

TriPLICATE 12-lead electrocardiograms (ECG) are to be collected at the timepoints specified in Schedule of Activities. The continuous (non-categorical) ECG test measured in triplicate includes heart rate, PR interval, QRS interval, QT interval, QTc interval using Fridericia's formula (QTcF) and RR interval. Each triplicate ECG is also interpreted as "normal", "abnormal" or "not evaluated". The number and percentage of participants with shifts from normal to abnormal will be summarized by treatment group. All postbaseline data will be used to identify abnormalities, regardless of whether a scheduled or unscheduled visit.

The mean of the triplicate continuous ECG parameter values at each nominal timepoint will be used for the analyses. If any triplicate within a nominal timepoint is abnormal, the interpretation will be counted as abnormal once for that nominal timepoint.

Actual values and change from baseline for the continuous (non-categorical) ECG parameters will be descriptively summarized by timepoint. Baseline for these analyses will be the mean of the replicate values from predose Day 1. If there are no replicates for predose Day 1, then the mean of the replicates from Screening will be used.

The number and proportion of participants whose QTcF results or change values meet certain predefined criteria (listed below) will be summarized.

- Absolute QTcF interval > 450 msec
- Absolute QTcF interval > 480 msec
- Absolute QTcF interval > 500 msec
- Changes from baseline QTcF >30 msec
- Changes from baseline QTcF > 60 msec

A listing of both qualitative and quantitative ECG data will be presented.

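### Part 1 SAP 5.7.3 counts vital-sign abnormalities against absolute cut-offs without regard to the baseline value, so new-onset and pre-existing findings are mixed, chiefly for blood pressure

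*SAP*

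**What the plan says.** Part 1 SAP 5.7.3 introduces the categorical vital-sign table with "The incidence of clinically significant post baseline abnormalities will be summarized per the criteria below". The blood-pressure lines read "Systolic blood pressure <90 mmHg or >140 mmHg or >160 mmHg" and "Diastolic blood pressure <50 mmHg or >90 mmHg or >100 mmHg". Temperature, pulse and respiratory rate are likewise fixed limits. Weight alone is tied to the participant's own starting value: "Weight 7% or more increase from baseline; 7% or more decrease from baseline". The section states neither a denominator nor how to treat someone who meets a criterion before the first dose. Protocol 13.3.1.3 adds no rule.

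Elsewhere the same SAP does condition on baseline. For laboratory low/high shifts, 5.7.2 says: "In each summary, the denominator for the percentage is the number of participants at risk for the shift", and defines at risk as a baseline not already low (or high) with at least one post-baseline value. Section 5.7.6 restricts treatment-emergent suicidal behavior to participants negative on all behavior items at baseline.

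The protocol's Benefit-Risk Analysis (Synopsis, repeated in 3.3) cites human genetic data suggesting that "variation in ATXN2 could be associated with changes in blood pressure and cardiometabolic phenotypes".

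**The concern.** A table of post-baseline incidence is normally read as what emerged after dosing. Under fixed limits with no baseline condition, a participant at 150 mmHg systolic before the first dose enters the >140 row at the next reading above 140. There are many such readings: on dosing days vital signs are taken predose and at 2 and 4 hours postdose (Part 1 Schedules of Activities, Tables 1 and 2). No Part 1 exclusion criterion names hypertension or sets a blood-pressure limit, so such participants can be enrolled.

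At stake is how clearly a blood-pressure effect would show. Participants who would cross the limit under either treatment add the same share to every column. That pulls the risk ratio toward 1 and shrinks the difference, in a parameter that the protocol itself flags.

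**Working it through.** The plan states no figure for this table, so there is none to reproduce. The check is an illustration.

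**Group sizes (protocol 5.3.1).** Active: 6 + 6 + 9 + 3 + 36 + 12 = 72. Placebo: 2 + 2 + 3 + 1 + 12 + 6 = 26. Total 98, as planned. The table's columns are 5 mg (6), 20 mg (6), 60 mg (9 + 3 = 12), 120 mg (36 + 12 = 48) and pooled placebo (26).

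**Assumptions (not in the documents).**
- b = share beyond the limit at baseline, 10% to 40%
- s = share of those beyond it again after baseline, 1 (0.8 as a check), equal in both arms
- i = new-onset incidence among the rest

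**Formulas.** Proportion as written = b·s + (1 − b)·i. At-risk proportion = i.

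**Level.** With s = 1 and i of 10% to 20%, the proportion as written runs from 0.10 + 0.90 × 0.10 = 19% to 0.40 + 0.60 × 0.20 = 52%. Between 36% and 87% of those counted were already beyond the limit at baseline (31% to 84% with s = 0.8).

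**Dilution.** Take i = 10% on placebo and 25% on active: difference 15 points, risk ratio 2.5. With s = 1:

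| b | Placebo | Active | Difference | Risk ratio |
|---|---|---|---|---|
| 10% | 0.190 | 0.325 | 13.5 points | 1.71 |
| 20% | 0.280 | 0.400 | 12.0 points | 1.43 |
| 30% | 0.370 | 0.475 | 10.5 points | 1.28 |
| 40% | 0.460 | 0.550 | 9.0 points | 1.20 |

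The difference is always (1 − b) × 15 points. With s = 0.8 it is unchanged, and the risk ratio is (0.08 + 0.225)/(0.08 + 0.09) = 1.79 at b = 10% and (0.32 + 0.15)/(0.32 + 0.06) = 1.24 at b = 40%.

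**Does an at-risk denominator also reduce noise?** Take b = 30% and s = 1, with the same i in both arms. The SD of the difference from placebo as written is √[p(1 − p)(1/n + 1/26)], where p = 0.30 + 0.70·i. At risk it is √[i(1 − i)(1/(0.7n) + 1/18.2)], since 0.7 × 26 = 18.2.

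| n | i = 15%: as written → at risk | i = 25%: as written → at risk |
|---|---|---|
| 6 | 22.2 → 19.3 points | 22.6 → 23.4 points |
| 12 | 17.1 → 14.9 points | 17.4 → 18.1 points |
| 48 | 12.0 → 10.4 points | 12.2 → 12.6 points |

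The SD falls modestly at 15% new onset and rises slightly at 25%. The gain is less dilution, not better precision.

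**The case against.** Several objections limit the point, and most of them stand.

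- **The SAP does not instruct anyone to count pre-existing abnormalities.** This stands. The rule is unspecified, and the mixing follows from applying the text literally. That is still a gap, because two programmers could build different tables.
- **The SAP is not generally inconsistent.** A reader might infer that at-risk denominators are its rule and vital signs the lone exception. The documents do not support that. The CSF white-cell and protein threshold proportions in 5.7.2 and the reflex proportions in 5.7.5 also lack a baseline condition.
- **QTcF is hardly affected.** The line "Absolute QTcF interval > 450 msec" has the same form, so it is tempting to include it. But Part 1 exclusion criterion 18 covers QTcF above 450 msec in males and 460 msec in females as part of clinically significant ECG abnormalities. That leaves mainly women between 450 and 460 msec and almost no one near 480 or 500. Section 5.7.4 also lists changes of more than 30 and 60 msec and counts normal-to-abnormal shifts. QTcF is not part of this point.
- **Other outputs cover part of the ground.** Part 1 also gives change from baseline by visit, a full listing, and paired limits (>140 and >160, >90 and >100) that show some worsening. Clinically significant results are reported as adverse events, for which a pre-existing condition counts only if it worsens. No test or decision rule rests on this table.
- **Baseline is not a diagnosis.** It is usually one Day 1 predose value, so a single high reading before a lumbar puncture would classify a participant as already abnormal.
- **An at-risk-only count could hide harm in Part 2.** The Part 2/integrated SAP (5.7) sets the Part 2 safety baseline at the first Part 2 dose. Up to 48 D1/D2 participants reach it after about six months on BIIB105. A rise that began in Part 1 would be classed as already present.

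**Conclusion.** The concern holds as a minor reporting gap in Part 1 SAP 5.7.3, mainly for blood pressure. Under the assumed inputs, a true new-onset risk ratio of 2.5 would appear as 1.71 to 1.20, and a 15-point difference as 13.5 to 9 points. These figures rest on an assumed baseline prevalence of 10% to 40%, assumed new-onset rates, and equal recurrence in both arms among those already beyond the limit. If few participants start beyond a limit, the effect is small.

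A reader might also infer that a restricted denominator would steady comparisons in the small dose groups. The calculation does not support that: the SD moves a few points either way. Nor does the point affect any formal inference, since these summaries are descriptive.

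**What to change.** In Part 1 SAP 5.7.3, add that each absolute criterion is tabulated by whether the baseline value met it:

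- New-onset incidence: participants not meeting the criterion at baseline who meet it at any post-baseline reading, divided by those not meeting it at baseline with at least one post-baseline value, as in the 5.7.2 shift tables.
- A separate column for those already meeting it at baseline, and how many meet it again, so that no one is dropped.

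Apply this line by line, so that a participant at 150 mmHg stays at risk for the >160 row. State how a missing baseline is handled; 5.7.2 includes shifts from unknown. Weight needs no change.

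Do not copy the at-risk-only count into the Part 2/integrated SAP with its present baseline. Any split there should use the value before the first BIIB105 dose, whichever part that falls in.

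The cost is a sentence or two in the SAP and extra columns in an existing table, with no new data. The downside is smaller denominators: with 30% beyond the limit at baseline, a six-person group leaves about four at risk (0.7 × 6 = 4.2), so one new case moves the figure by about 25 points (1/4) rather than 17 (1/6). Showing counts beside percentages makes this plain.
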